6.4. Trial intervention

The intervention arm to which each participating site is randomised will be offered to all eligible surgical patients for the duration of the trial.

Intervention arm

Participating sites which have been randomised to increased surveillance will need to provide increased surveillance to surgical patients with a predicted increased

postoperative risk as determined by the ASOS Surgical Risk Calculator⁹ stratification tool (also available at www.asos.org.za). Increased postoperative surveillance can include any of the following; i) admission to a higher care ward than had been planned at the time of surgery, ii) an increase in the frequency of nursing observations in the postoperative period, iii) ensuring that the patient is assigned to a bed in view of the nursing station, and not in a remote location in the postoperative ward, or iv) allowing family members to stay with the patient in the ward in the postoperative period. The nature of the offered increased postoperative surveillance will be left to the discretion of the healthcare workers and the participating sites. However, all sites will be encouraged to include more than one of the increased postoperative surveillance intervention. The healthcare providers will also receive information on the leading causes of postoperative mortality in African surgical patients as documented in ASOS; surgical site infections, bloodstream infection and acute respiratory distress syndrome, pneumonia, acute kidney injury, postoperative bleeding, and cardiac arrest.⁸ This will be known as the 'Postoperative surveillance bedside guide' and will be placed at the bedside of every patient flagged as high-risk by the ASOS Surgical Risk Calculator.⁹ This should be placed in a visible position at the patient's bedside e.g. posted on the wall above the patient's bed.

Control arm

Participating sites randomised to the control arm will provide usual postoperative care to patients. The care will be left to the discretion of the healthcare providers.

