7.1. Sample size calculation

This is a cluster randomised trial of hospitals in Africa. We will match hospitals on expected surgical volume in a week of surgery. This varied tremendously across the ASOS group; with a median number of surgical procedures per hospital for the study week in ASOS of 29 (IQR 10-71).⁸ The variability of the individual patient outcomes explained by the cluster (or surgical site) is taken into account in these sample size calculations. The intra-cluster correlation coefficient (ICC) in ASOS was 0.01. For the sample size calculation, we have therefore used a conservative ICC of 0.015.

Based on ASOS, we estimate the coefficient of variance for a 4-week recruitment period to be 0.63. A 4-week recruitment period is defined as the following; i) hospitals stop recruiting at the end of the week in which they have exceeded 100 enrolled patients, and ii) if a site had not reached 100 enrolled patients after 4 weeks of recruiting, it would stop recruiting.

The incidence of mortality in ASOS was 2.1%.⁸ We expect a 25% relative risk reduction in mortality through increased surveillance of postoperative surgical patients at high-risk of severe complications or in-hospital mortality. Based on the intra-cluster correlation coefficient (ICC) for the composite of severe complications and mortality in ASOS-2 of 1.5%, a coefficient of variance of 0.63, and stratification for the level of the surgical facility, and the volume of procedures per week, a trial for efficacy of increased postoperative surveillance would require 64,200 patients, from 642 surgical centres across Africa (Table 1).⁸ Based on a relative risk reduction of 25% in the intervention arm, the sample sizes for the primary outcome are shown in Table 1.

TABLE 1: Sample size calculations for the ASOS-2 Trial based on a power of 80%, 2-sided $\alpha = 0.05$ and a mean cluster size of 100 patients

Primary outcome (in-hospital all-cause mortality)					
Control event rate	Intervention arm	Relative risk	Intra-cluster correlation coefficient (ICC)	Coefficient of variance (CV)	Total clusters
2.0%	1.5%	0.75	0.015	0	536
2.0%	1.5%	0.75	0.015	0.63	664
2.0%	1.6%	0.80	0.015	0.63	1068

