- IV A patient with severe systemic disease that is a constant threat to life
- V A patient who is not expected to survive for 24 hours without the operation.

Urgency of surgery

Elective: Not immediately life-saving; planned within months or weeks.

Urgent: Planned surgery within hours or days of the decision to operate.

Emergency: As soon as possible; no delay to plan care; ideally within 24 hours.

Severity of the surgery

This is the category of surgery which indicates a combination of complexity and amount of tissue injury.

Minor surgery would include procedures lasting less than 30 minutes performed in a dedicated operating room which would often involve extremities or body surface or brief diagnostic and therapeutic procedures eg arthroscopy without intervention, removal of small cutaneous tumour, diagnostic proctology, biopsy of small lesions, etc.

Intermediate procedures are more prolonged or complex that may pose the risk of significant complications or tissue injury. Examples include laparoscopic cholecystectomy, arthroscopy with intervention, bilateral varicose vein removal, tonsillectomy, inguinal hernia repair, breast lump resection, haemorrhoidectomy, appendicectomy, partial thyroidectomy, cataract surgery, uvuloplasty, minimally invasive repair of vaginal prolapse, vaginal hysterectomy, tendon repair of hand, fixation of mandibular fracture, etc.

Major surgical procedures are expected to last more than 90 minutes and include major gut resection, major joint replacement, mastectomy, extensive head and neck tumour resection, abdominal aortic aneurysm repair, major vascular bypass procedure, procedures involving free flap to repair tissue defect, amputation, total thyroidectomy, cystectomy, trans-urethral resection of prostate, resection of liver tumour, carotid endarterectomy, nephrectomy, total abdominal hysterectomy, spinal discectomy, etc.

Definitions of postoperative care

Post anaesthesia care unit (PACU):

A postoperative recovery ward or unit which is dedicated to providing increased postoperative care during recovery (both in intensity of monitoring and in duration of care), when compared to normal postoperative recovery care.

High care ward:

A postoperative ward which is dedicated to providing increased postoperative care, when compared to the normal postoperative surgical ward.

Increased frequency of nursing observations:

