Nursing observations which are conducted more frequently, than the normal frequency of observations on the postoperative ward.

Patient's bed in view of the nurses' station:

The patient is positioned in a bed close to the nursing station to ensure that the nurses can always see the patient from the nursing station.

Family members to stay with the patient in the ward:

If the family members are asked to stay with the patient on the ward, because of a concern that the patient is at increased risk of death or morbidity in the postoperative period.

Definitions of severe surgical complications

The following definitions and grading are provided for guidance where the nature and severity of a possible complication following surgery is uncertain. These definitions are based on the 'Standards for definitions and use of outcome measures for clinical effectiveness research in perioperative medicine: European Perioperative Clinical Outcome (EPCO) definitions: a statement from the ESA-ESICM joint taskforce on perioperative outcome measures'.¹

Definition of a 'Severe Complication'

Results in significant prolongation of hospital stay and/or permanent functional limitation or death. Almost always requires clinical treatment.

Surgical site infection (superficial)

Infection involving only superficial surgical incision which meets the following criteria:

1. Infection occurs within 30 days after surgery and
2. Involves only skin and subcutaneous tissues of the incision and
3. The patient has at least one of the following:
 - a. purulent drainage from the superficial incision
 - b. organisms isolated from an aseptically obtained culture of fluid or tissue from the superficial incision and at least one of the following signs or symptoms of infection: pain or tenderness, localized swelling, redness, or heat, or superficial incision is deliberately opened by surgeon and is culture positive or not cultured. A culture-negative finding does not meet this criterion.
 - c. diagnosis of a incisional surgical site infection by a surgeon or attending physician

Surgical site infection (deep)

An infection which involves both superficial and deep parts of surgical incision and meets the following criteria:

1. Infection occurs within 30 days after surgery if no surgical implant is left in place or one year if an implant is in place and

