4. Radiological or echocardiographic evidence of new loss of viable myocardium or new regional wall motion abnormality
5. Identification of an intra-coronary thrombus at angiography or autopsy

Pulmonary embolism (PE)

A new blood clot or thrombus within the pulmonary arterial system.

Guidance: Appropriate diagnostic tests include scintigraphy and CT angiography. Plasma D-dimer measurement is not recommended as a diagnostic test in the first three weeks following surgery.

Stroke

Embolic, thrombotic, or haemorrhagic cerebral event with persistent residual motor, sensory, or cognitive dysfunction (e.g. hemiplegia, hemiparesis, aphasia, sensory deficit, impaired memory).

Hospital resource use after surgery

We will collect some basic data to describe the treatment resources patients received after surgery.

Critical care admission to treat postoperative complications:

Postoperative complications requiring admission to critical care to treat the postoperative complications or provide critical care support necessitated by the severity of the postoperative complications.

Days in hospital after surgery: Total number of days in hospital after surgery.

Status at hospital discharge or 30th postoperative in-hospital day: The survival status of the patient at hospital discharge, or at the 30 in-hospital day (if the patient had not yet been discharged following surgery). The study is censored at the 30th in hospital postoperative day.

Reference

Appendix 2

African Surgical OutcomeS-2 (ASOS-2) Trial: Hospital 'broadcasting' signage

IMPORTANT PATIENT INFORMATION

A research study is being conducted atHospital.

The research is being done by Dr from the Department of

Why is this research study being done?

To understand if increasing monitoring following surgery, makes surgery safer.

Why are we telling you about this study?

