3.2. Analysis population

Primary analysis will be by modified intention to treat population which includes all patients recruited from randomised hospitals where the hospital reported any patient data. Hospitals that are randomised, but do not submit any patient data will be excluded from the modified intention to treat analysis on the presumption that there is no risk of exposure to the trial intervention. Patients will be analysed in the treatment group to which their hospitals were originally allocated.

Secondary analyses will include two analytic approaches to two per protocol populations. Refer to table: Secondary analyses based on implementation fidelity. In the first per protocol analysis we will compare all patients from hospitals with data in the standard of care arm to all patients from hospitals with data in the intervention arm where the intervention hospital provided the intervention with fidelity to at least 80% of high-risk patients. Patients from hospitals in the intervention arm where the hospital delivered the intervention with fidelity to fewer than 80% of patients will be excluded from this analysis. In the second per protocol analysis we will compare all patients from hospitals with data in the standard of care arm to all patients from hospitals in the top two tertiles of implementation fidelity. Patients from intervention hospitals in the bottom tertile of implementation fidelity will be excluded from this analysis. At the hospital level we will report implementation fidelity as the proportion of high-risk patients who received the intervention with fidelity. We use two definitions for implementation fidelity; i) provision of at least the high-risk bedside guide plus one additional component of the intervention on days 0 and 1 postoperatively and ii) provision of at least 2 components of the intervention on days 0 and days 1 postoperatively, regardless whether the high-risk bedside guide is one of the components.

Secondary analyses based on implementation fidelity		
	Fidelity = High-risk individuals exposed to the bedside guide plus at least 1 additional component of the intervention	Fidelity = High-risk individuals exposed to at least 2 components of the intervention, regardless whether one is the bedside guide
Intervention hospitals where >= 80% of high-risk patients received the intervention with fidelity	Per protocol analysis 1	Per protocol analysis 3

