3.2.3. Patient risk factors and patient level analysis

A prespecified patient level analysis will be undertaken including all high-risk individuals with data in a standard of care hospital, and all high-risk individuals in an intervention arm who can be presumed to be exposed to the intervention (definition 1: poster and one other intervention on day 0 and day 1; definition 2: any 2 interventions on day 0 and day 1). The relative risk of experiencing the primary (secondary) outcome by exposure to intervention (as defined above) will be estimated in stratified models for the following individual characteristics:

- I. age (years)
- II. ASA status (1-5)
- III. surgical procedure category (Gynaecologic, Obstetric, Neuro, ENT, Orthopaedic, Plastics and Breast, Urology, Gastrointestinal and Hepatobiliary, Cardiothoracics, Other)
- IV. indication for surgery (non-communicable disease, caesarean section, trauma, infection)
- V. urgency of surgery (elective, urgent, emergent)
- VI. severity of surgery (minor, intermediate, major)

This concludes the pre-specified analyses for ASOS-2. Further exploration of the data will take place.

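### Fidelity definition 2 counts some usual care and some reactive day-0 care as delivery, so the secondary analyses built on it can be biased in either direction

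*Combined protocol and SAP*

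**What the plan says.** Protocol 6.4 lists four surveillance components: a higher care ward, more frequent nursing observations, a bed in view of the nursing station, and family staying on the ward. A bedside guide is added for high-risk patients. The SAP (3.2 Analysis population) sets two fidelity definitions. Definition 1 needs the guide plus one other component on days 0 and 1. Definition 2 needs "provision of at least 2 components of the intervention on days 0 and days 1 postoperatively", and the guide need not be one of them. Definition 2 drives per-protocol analyses 3 and 4, which keep intervention hospitals with at least 80% fidelity or in the top two fidelity tertiles. It returns in SAP 3.2.3 as "definition 2: any 2 interventions on day 0 and day 1". In each case the intervention patients or hospitals that pass are compared with all control patients, or all high-risk control patients, with data.

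The ward component in 6.4 is "admission to a higher care ward than had been planned at the time of surgery". Appendix 1 defines a high care ward as "A postoperative ward which is dedicated to providing increased postoperative care, when compared to the normal postoperative surgical ward". On family presence, 6.4 speaks of allowing relatives to stay, while Appendix 1 requires that they be asked "because of a concern that the patient is at increased risk of death or morbidity in the postoperative period". The intervention CRF asks Yes or No by day, without either condition. Appendix 1 also defines critical care admission to treat complications ("Postoperative complications requiring admission to critical care to treat the postoperative complications"), but the intervention CRF has no field for it.

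**The concern.** Definition 2 can be met without any trial-specific action. The control CRF records the same four care items, so the trial itself expects them to occur under usual care. A patient already booked for high care and placed in view of the nurses can pass with no change in care. So can a patient who deteriorates on day 0 and is moved and observed more closely. An unplanned transfer fits even the 6.4 wording, and nothing in the SAP excludes it.

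Because the rule is applied in one arm only, those who pass are a selected group set against an unselected one. The only model the SAP names is a univariable GEE (3.2.1). SAP 3.2.3 stratifies on baseline characteristics, and Protocol 7.2 mentions including the risk-calculator factors. None of these removes confounding by what happens after surgery. At stake is how a neutral or surprising result is explained: Protocol 7.3 makes fidelity an explicit aim and asks why the intervention does or does not change outcomes.

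**Working it through.** **1. The plan's own figure.** The documents give no figure for the fidelity analyses. The hospital-level check below borrows the sample-size inputs, so those were reproduced first. Table 1 is "based on a power of 80%, 2-sided $\alpha = 0.05$ and a mean cluster size of 100 patients", and the relevant row reads "2.0% 1.5% 0.75 0.015 0.63 664". The pooled two-proportion formula for 2.0% vs 1.5% gives 10,795 per arm. The design effect is 1 + ((1 + 0.63²) × 100 − 1) × 0.015 = 3.080. Clusters = 2 × 10,795 × 3.080 / 100 = 665, against 664 stated. It reproduces.

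**2. The component wording side by side.**

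| Component | Protocol 6.4 | Appendix 1 | Intervention CRF |
|---|---|---|---|
| Ward | Higher than planned at surgery | Any ward giving more care than the normal surgical ward | Yes/No by day |
| Observations | An increase in frequency | More often than the ward norm | Yes/No by day |
| Bed | In view of the nursing station | Close to the station, always visible | Yes/No by day |
| Family | Allowed to stay | Asked to stay because of concern | Present, Yes/No by day |

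The CRF has no field for planned care, for the reason for a step-up, or for whether the trial prompted it.

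**3. Patient level (3.2.3), simple illustration with no treatment effect.** All inputs are assumptions: high-risk mortality 8%; 50% exposed regardless of outcome; among the rest, 30% of those who die and 5% of survivors are stepped up from day 0. Let q be the share of deaths on day 0; those patients cannot meet the day-1 requirement.

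- Exposed deaths = 0.08 × (1 − q) × (0.5 + 0.5 × 0.30) = 0.052 × (1 − q)
- Exposed survivors = 0.92 × (0.5 + 0.5 × 0.05) = 0.483
- q = 0: 0.052 / 0.535 = 9.7%; RR = 9.7 / 8.0 = 1.21
- q = 10%: 0.0468 / 0.5298 = 8.8%; RR 1.10
- q = 20%: 0.0416 / 0.5246 = 7.9%; RR 0.99

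With 80% truly exposed, q = 0 gives 0.0688 / 0.8140 = 8.5%, RR 1.06. With q = 10% it is 0.0619 / 0.8071 = 7.7%, RR 0.96.

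**4. Patient level, wider assumptions.** A share d (5–10%) deteriorates on day 0 with R times the mortality (5–10). Usual care gives two components to u0 of stable patients (10–30%) and u1 of deteriorating ones (60–80%). The trial prompts delivery in a share t. With e0 = 1 − (1 − t)(1 − u0), e1 = 1 − (1 − t)(1 − u1) and no day-0 deaths:

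RR = {[(1 − d)e0 + dR·e1] / [(1 − d)e0 + d·e1]} / [(1 − d) + dR].

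Example (d = 0.05, R = 5, u0 = 0.1, u1 = 0.6, t = 0.5): (0.7225 / 0.5625) / 1.2 = 1.07. Day-0 deaths are then removed from the exposed group only. Ranges over four input sets:

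| Trial-prompted delivery | No day-0 deaths | 10% of deaths on day 0 | 20% of deaths on day 0 |
|---|---|---|---|
| 0% | 1.15–2.53 | 1.05–2.32 | 0.94–2.11 |
| 20% | 1.08–1.54 | 0.98–1.40 | 0.88–1.26 |
| 50% | 1.04–1.18 | 0.94–1.07 | 0.84–0.96 |
| 80% | 1.01–1.05 | 0.92–0.95 | 0.82–0.85 |

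If usual care is unrelated to deterioration (10% in both groups), the RR is 1.00, 0.91 and 0.81 across the three columns.

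**5. Hospital level (analyses 3 and 4).** Simulation with no effect: 332 hospitals per arm, mortality 2%, ICC 0.015, cluster-size CV 0.63, 20% of patients high-risk (assumption), ratio estimator with cluster-robust standard errors rather than the SAP's GEE, 600 runs per scenario.

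- Reactive care alone: RR 1.02–1.06 (tertiles) and 1.02–1.03 (80% rule). False harm occurred in 4.7–8.3% of runs (nominal 2.5%).
- Recorded fidelity, standing for usual-care level, correlated with hospital mortality at +0.3: RR 1.12 and 1.27, with false harm in 21% and 46% of runs.
- Correlation −0.3: RR 0.87 and 0.74, with false benefit in 27% and 53%.
- Zero correlation: RR about 1.00 under both rules.

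**The case against.** The strongest reply is that little rests on this. The primary analysis is by hospital allocation and uses no fidelity measure. Definition 1, which requires the trial-specific guide, is reported alongside definition 2. The process evaluation in Protocol 7.3 adds site visits and interviews. All of that stands and limits the weight of the point, though definition 1 shares the problem for its one additional component.

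The days 0 and 1 requirement also blunts the rescue argument. A transfer to treat a complication helps a patient qualify only if it happens on day 0, and nothing in the documents supports a particular share of such transfers. That stands too, and it is why no fixed size or direction can be claimed. At hospital level the reactive effect is small. The larger figures come from assumed correlations and describe the ordinary hazard of selecting hospitals by performance, to which definition 2 adds selection by usual care.

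Finally, a reader might infer that a hospital with routine family presence and visible beds would score 100% fidelity with no change in care. Appendix 1 does not support that: relatives count only if asked to stay because of concern. It could happen only if staff completed the CRF from its label alone. The ward and bed items carry no such safeguard in Appendix 1.

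**Conclusion.** The mismatch between 6.4, Appendix 1 and the CRF is real. Definition 2 therefore measures exposure with misclassification. Under a true null, analyses 3 and 4 and the definition 2 version of 3.2.3 can be biased either way. Day-0 escalation pushes toward harm, the day-1 requirement pushes toward benefit because the earliest deaths cannot qualify, and selection of hospitals by usual-care level can go in either direction. The patient-level bias from reactive care shrinks as true delivery rises. Every size above rests on exposure, deterioration and day-0 death rates that the documents do not give.

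Three stronger readings are tempting and not supported. The first is that definition 2 does not measure exposure at all; it does so imperfectly. The second is that it will show harm; the RR of 1.21 holds only with no day-0 deaths. The third is that a neutral trial could not be interpreted; definition 1 and the process evaluation still bear on that. This is a cheap improvement to secondary analyses, not a threat to the primary result.

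**What to change.** 1. Reconcile the component wording across Protocol 6.4, Appendix 1 and the CRF, and add a CRF item for whether a higher-care admission was to treat a complication. Rewording the ward item alone would not separate rescue. The SAP was added on 19 March 2020 and recruitment was to end that month, so this helps only patients still to be recruited.

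2. In SAP 3.2.3, use a landmark at the end of day 1 in both arms: high-risk patients alive, in hospital and free of a severe complication through day 1. Complication day, days in hospital and discharge status are already on the CRF. Do not instead discount, in the intervention arm alone, components that follow a complication. If the composite outcome were 20% with a tenth of events on day 0 (assumptions), that rule would give a null RR of (0.18 / 0.98) / 0.20 = 0.92, a false benefit.

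3. Tabulate, by arm, the proportion of high-risk patients with at least two of the four care components ever recorded. Read definition 2 results, including analyses 3 and 4, against that difference and label them descriptive. Ever recorded is the safe basis because part of the control CRF was not available for this review, so a day-by-day grid there could not be confirmed.

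The cost is small CRF edits, some SAP wording and one table. The downsides are fewer patients in 3.2.3, early events left out of it, and somewhat lower reported fidelity. The landmark does not remove step-up for deterioration not yet recorded as a severe complication, which is a further reason for the descriptive label.
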